#### 9.4.3.2 Adverse Events

Treatment-emergent adverse events (TEAEs), defined as those AEs occurring after the first administration of study treatment until the last study visit, will be tabulated in frequency tables by System Organ Class and Preferred Term based on the Medical Dictionary for Regulatory Activities (MedDRA) for each study phase. Additional summary tables will be provided for SAEs, AEs related to the study drug and/or study procedure, AESIs, and AEs leading to treatment discontinuation and study withdrawal. For a given AE, a subject will be counted once even if he/she has experienced multiple episodes of that particular AE.

Pre-treatment AEs will be listed separately.

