3.3. Brief Description

[figure not shown]
This is an open-label, single-group study to evaluate the PK and safety of 30 mg of nemolizumab in adolescent subjects (12 to 17 years of age), with moderate-to-severe AD and associated pruritus. Approximately 20 eligible subjects will be enrolled to receive subcutaneous injections of nemolizumab (30 mg) every 4 weeks over a 16-week treatment period, with a loading dose of 60 mg on Day 1.

Study participation may include a total of 28 weeks for subjects that complete the screening, treatment and follow-up periods. This study includes a 2 to 4-week run-in period followed by a 16-week treatment period. A follow-up visit (Week 24) is scheduled for subjects who will not immediately rollover (within 7 days following the Week 16 visit) into the nemolizumab open-label extension study. Subjects who prematurely discontinue the study before the Week 16 visit have to be followed for 12 weeks after their last dose of study drug.

Subjects will be screened and complete a run-in period of at least 14 days prior to the Baseline visit. Starting on Baseline/Day 1, all eligible subjects will receive nemolizumab administered subcutaneously, in the presence of background TCS therapy. A loading dose of nemolizumab (60 mg) is administered on Day 1, with subsequent nemolizumab dosing of 30 mg occurring every 4 weeks. The final dose of study medication will occur at Week 12 and subjects will complete the treatment period at the Week 16 visit. An 8-week follow-up period is scheduled (Week 24 visit) for subjects who do not immediately rollover (within 7 days following the Week 16 visit) into the nemolizumab open-label extension study. Subjects who prematurely discontinue the study prior to the Week 16 visit have to be followed for 12 weeks after their last dose of study medication.

Assessments of PK, safety, and efficacy will be conducted throughout the study. Subject-reported assessments of pruritus, sleep disturbance and use of topical medication for their eczema will be collected daily.

Figure 1 below shows a description of the Study Design:

: Nemolizumab administration

* : Loading dose (60 mg) at baseline

Abbreviations: BL = Baseline; n = number of subjects; q4w = every 4 weeks; TCS = topical corticosteroid; W =week.

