5.2. Safety Population

The Safety Population will include all subjects in the ITT who were administered at least one dose of study medication. Subjects will be analyzed according to the treatment actually received.

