10.2. Adverse Events

Adverse events (AEs) will be coded using the Medical Dictionary for Regulatory Activities (MedDRA) Version 21.1. Summaries of AEs will include only treatment emergent AEs (TEAEs) defined as AEs with an onset date/time on or after the date/time of first treatment. AEs with completely missing onset dates/time will be considered as TEAEs. If AE onset date/time is partially missing, the AE will be considered as TEAE unless the non-missing part of date/time proves it started prior to the first treatment date/time.

AEs will be summarized using the number and percent of subjects reporting each system organ class (SOC) and preferred term (PT) and sorted alphabetically by SOC and by descending frequency of PT within SOC. Subjects who experienced multiple events within the same SOC will be counted once in the SOC summary. Subjects who experienced multiple occurrences of events with the same PT will be counted once in the PT summary. Percentages will be calculated using the total number of subjects in the Safety population.

The following summary tables for AEs will be presented:

- Overall Summary of Treatment Emergent Adverse Events (TEAEs), All Causalities
- Overall Summary of Treatment Emergent Adverse Events (TEAEs), Study Drug Related
- Treatment-Emergent Adverse Events (TEAEs) by System Organ Class and Preferred Term, All Causalities
- Treatment Emergent Adverse Events (TEAEs) by System Organ Class and Preferred Term,
 Study Drug Related
- Serious Treatment-Emergent Adverse Events (TEAEs) by System Organ Class and Preferred Term, All Causalities
- Serious Treatment Emergent Adverse Events (TEAEs) by System Organ Class and Preferred Term, Study Drug Related

- Treatment-Emergent Adverse Events (TEAEs) by System Organ Class, Preferred Term, and Maximum Severity, All Causalities
- Severe Treatment Emergent Adverse Events (TEAEs) by System Organ Class and Preferred Term, All Causalities
- Severe Treatment Emergent Adverse Events (TEAEs) by System Organ Class and Preferred Term, Study Drug Related
- Treatment-Emergent Adverse Events (TEAEs) Leading to Permanent Discontinuation of Study Drug by System Organ Class and Preferred Term, All Causalities
- Treatment Emergent Adverse Events (TEAEs) Leading to Permanent Discontinuation of Study Drug by System Organ Class and Preferred Term, Study Drug Related
- Treatment-Emergent Adverse Events (TEAEs) of Special Interest by System Organ Class and Preferred Term, All Causalities

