10.9. Other Safety

Confirmed pregnancy test results, childbearing potential, premense status results, biomarker and virology assessment data will be presented in a listing.

11. Immunogenicity

Blood samples will be collected to assess anti-drug (anti-nemolizumab) antibodies (ADA). Serum samples will be assessed for ADA at Baseline, Weeks 4, 8, 16, 24 and at any unscheduled visit for safety reasons.

Screening ADA, confirmation ADA, ADA titer, nutralizing antibodies, and treatment-related ADA will be will be summarized for the Safety population (scheduled visits only).

A treatment-related ADA is a post-baseline confirmatory ADA sample showing positive results while the baseline sreening or confirmatory ADA sample shows negative results.

All Immunogenicity data will be listed for the Safety population.

12. Health Economics

Not applicable.

13. Interim Analyses

An interim analysis is planned after approximately 10 subjects complete the Week 8 visit. The study will attempt to enrol at least 3 subjects with a low body weight (≤ 61 kg) for the interim analysis and approximately 6 total subjects with low body weight for the overall study population, with investigators attempting to enrol subjects at the lower age range (12-14 years old). The interim analysis will assess whether the observed safety and PK data from adolescents are similar to the data obtained in adults, which is the basis for allowing recruitment of adolescent subjects into the planned nemolizumab Phase 3 studies for AD (pivotal and open-label extension protocols).

Outputs presented for the interim analysis and for the IDMC are marked in Sections 18 (Index of Tables), Section 19 (Index of figures) and Section 20 (Index of Listings). But the selected output list for IDMC meeting can be updated by IDMC member's request.

14. Changes from Analysis Planned in Protocol

No changes to the methods planned in the protocol are foreseen.

15. Reference List

Not applicable.

16. Programming Considerations

All TLFs and statistical analyses will be generated using SAS® 9.4 or higher (SAS® Institute Inc., Cary, NC, USA). Computer-generated table, listings and figures (TLF) output will adhere to the following specifications.

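### The SAP sets no interim data cut for safety, so crude TEAE percentages from unequal follow-up would read too low against adult figures from a longer window

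*SAP*

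**What the plan says.** **Trigger and purpose.** SAP Section 13 (also Section 2.2, and Protocol Sections 7.1 and 9) says "An interim analysis is planned after approximately 10 subjects complete the Week 8 visit". On purpose it says "The interim analysis will assess whether the observed safety and PK data from adolescents are similar to the data obtained in adults", and this is the stated basis for admitting adolescents to the Phase 3 studies.

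**Planned course.** SAP Section 3.3: "Approximately 20 eligible subjects will be enrolled to receive subcutaneous injections of nemolizumab (30 mg) every 4 weeks over a 16-week treatment period".

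**Population.** SAP Section 5.2: "The Safety Population will include all subjects in the ITT who were administered at least one dose of study medication". There is no minimum follow-up.

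**Metric.** SAP Section 10.2 counts subjects with events, and "Percentages will be calculated using the total number of subjects in the Safety population". TEAEs are "AEs with an onset date/time on or after the date/time of first treatment", with no upper day. Protocol Section 9.4.3.2 has them "defined as those AEs occurring after the first administration of study treatment until the last study visit".

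**Interim outputs.** The SAP index of tables marks the overall, serious, severe, discontinuation and special-interest TEAE tables (14.3.1.1.1 to 14.3.1.2.12) for the interim, all on the Safety Population. The exposure summary (14.1.5.1), the drug administration listing (16.2.5.1) and the TEAE listing (16.2.7.1) are also marked.

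**Interim data cut.** SAP Section 9.2 gives one for PK only: the first ten subjects, with concentrations up to Week 8. I found no equivalent for safety. There is also no pause in enrolment, common TEAE window, person-time rate, adult comparison table or criterion for similarity.

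**The concern.** A cumulative percentage of subjects with an event cannot fall as follow-up lengthens. At the trigger, follow-up will range from 8 weeks or more in about ten subjects down to days in any just dosed. Under the rules as written, all of them count fully in the denominator. The interim percentage therefore depends partly on how fast the sites enrolled, which has nothing to do with the drug.

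Against an adult percentage from a longer window, the error can run in only one direction: adolescents look as safe as adults, or safer. That matters because safety is half of the similarity judgement that opens Phase 3 to adolescents. Protocol Section 7.3.1 regards 16 weeks of treatment as adequate for evaluating safety, whereas the interim assures only 8 weeks in about half the planned sample.

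**Working it through.** The plan gives no event rate, power or accrual figure to reproduce; the sample size was set without formal powering. What follows is an illustration.

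**Inputs from the documents.** About 20 subjects; trigger when about 10 complete Week 8; 16-week course; Safety Population denominator.

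**Assumptions not in the documents.** Evenly spaced entry, one subject every *g* weeks (*g* = 0.5, 1, 2 or 3); no dropout; adolescent hazard equal to adult hazard; adult percentage read at 16 weeks.

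**Step 1: follow-up at the trigger.** The tenth subject enters at 9*g*, so the cut-off is 9*g* + 8 weeks. Subject *i* (from 0) has been followed for 9*g* + 8 − *ig* weeks, capped at 16 for the mean.

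| One subject every | Dosed | Under 16 weeks | Under 8 weeks | Mean follow-up (weeks) |
|---|---|---|---|---|
| 0.5 week | 20 | 20 | 10 | 7.8 |
| 1 week | 18 | 16 | 8 | 8.4 |
| 2 weeks | 14 | 8 | 4 | 10.9 |
| 3 weeks | 12 | 5 | 2 | 12.7 |

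The 1-week and 2-week rows each include one subject dosed on the cut-off day.

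**Step 2: expected crude percentage.** With a constant hazard, p(t) = 1 − (1 − p16)^(t/16), averaged over all dosed subjects. For p16 = 50% and one subject per week, follow-up is 0, 1, ..., 15, 16 and 16 (capped) weeks. The sum of 0.5^(t/16) is 11.793 + 2 × 0.5 = 12.793, and 1 − 12.793/18 = 28.9%.

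| True 16-week incidence | 0.5 week | 1 week | 2 weeks | 3 weeks |
|---|---|---|---|---|
| 10% | 5.0% | 5.4% | 6.8% | 8.0% |
| 30% | 15.7% | 16.6% | 20.9% | 24.1% |
| 50% | 28.0% | 28.9% | 35.5% | 40.9% |
| 70% | 42.9% | 43.0% | 51.4% | 58.5% |

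At 50% the shortfall is 9.1 to 22.0 points; at 10% it is 2.0 to 5.0 points.

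**Step 3: other readings of the safety data set (true 50%).** The first ten subjects, followed to the calendar cut-off, would read 35.7% to 46.3%. The first ten, cut at Week 8, would read 1 − 0.5^(8/16) = 29.3%. Both stay below 50%, so restricting to ten subjects does not by itself remove the problem.

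**Step 4: hazard shape.** If events cluster early, with p(t) = 1 − (1 − p16)^((t/16)^0.5), the all-dosed figure for a true 50% is 36.1% to 44.5%. The shortfall narrows to 5.5 to 13.9 points.

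**Step 5: does the exposure table repair it?** SAP Section 10.1 defines duration as last injection minus first injection plus 1 day. A subject injected once, 27 days before the cut-off, is credited with 1 day. This is not time at risk and cannot be used to correct the percentages.

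**Step 6: after the fix.** With Day 1 to Day 57 in both groups and equal hazards, a true 16-week 50% reads 29.3% against 29.3%, and 30% reads 16.3% against 16.3%.

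**The case against.** The strongest reply is that the bias is conditional. Accrual is not stated. The adult event rates and follow-up length are not in the readable text, and nothing says that crude adolescent percentages will be set beside full-course adult ones; a same-window adult cut is not ruled out. The safety data set is unstated rather than declared to be all treated subjects, and the sponsor may mean the PK cut to apply to safety too. All of this stands, and it limits what can be claimed about size.

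A reader might infer that most interim subjects will be far short of 16 weeks. The documents do not support that: at one subject every 3 weeks only 5 of 12 are below 16 weeks. A reader might also infer a shortfall of a particular size against adults. That would need an adult window and event rate that cannot be read here.

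It is also fair that, with at most about 20 subjects, the interim exposure table and subject listings let a careful reader see who was dosed recently, and that the IDMC reviews safety separately. Visibility helps but does not adjust the percentages. Precision is poor in any case: 3 of 10 has an exact 95% interval of 6.7% to 65.2%, and 0 of 10 has an upper limit of 30.8%. Wide intervals do not excuse a one-directional error that is easy to avoid.

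**Conclusion.** The point holds in a conditional form. The interim safety data set is undefined. The SAP's general rules, applied as written, give percentages that depend on accrual and can only match or fall below those from a longer adult window when the hazards are equal. This goes beyond missing detail, because the default rules produce a specific and misleading metric for a stated decision.

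The figures of about 28% to 41% for a true 50%, and 5% to 8% for a true 10%, rest on a constant hazard, even accrual at one subject per 0.5 to 3 weeks, no dropout and a 16-week adult window. Slower accrual or early clustering of events would shrink the gap, and an adult window matched to the interim would remove most or all of it. The change should be made, with medium confidence in its practical effect.

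**What to change.** In SAP Sections 13 and 10.2:

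1. State the cut-off date for interim safety data.
2. Add TEAE, SAE and AESI tables limited to Day 1 to Day 57, for all subjects whose first dose was at least 8 weeks before the cut-off. Define membership by time since first dose, not by attendance at Week 8, so that subjects who stopped drug or left early (including for an adverse event) stay in.
3. For all treated subjects, add exposure-adjusted rates: subjects with a first event per patient-week at risk. Time at risk runs from first dose to the first event or, if there is none, to the earlier of the cut-off and last contact. This needs a new follow-up variable; the existing treatment duration will not serve.
4. Compare with adult 30 mg data over the same window and on the same metric. Matching the window matters for the rates too, since they are equal under equal hazards only if the hazard is constant or the windows agree.
5. Keep the all-subject tables for IDMC surveillance.

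The cost is SAP wording, some programming and a re-cut of adult data. No patients or visits are added. Recently dosed subjects would contribute only to the exposure-adjusted rates and the all-subject tables.

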16.1. General Considerations

- A separate SAS program will be created for each output.
- Each output will be stored in a separate file.
- Output files will be delivered in Word rtf format.
- The final TLFs will be provided in a combined pdf document including a table of contents which are hyperlinked to each output.
- Numbering of TLFs will follow International Conference on Harmonization (ICH) E3 guidance

16.2. Table, Listing, and Figure Format

16.2.1. General

- All TLFs will be produced in landscape format, unless otherwise specified.
- All TLFs will be produced using the Courier New font, size 8.
- The data displays for all TLFs will have a 1.5-inch binding margin on top of a landscape oriented page and a minimum 1-inch margin on the other 3 sides.
- Headers and footers for figures will be in Courier New font, size 8.
- Legends will be used for all figures with more than 1 variable, group, or item displayed.
- TLFs will be in black and white (no color), unless otherwise specified.
- Specialized text styles, such as bolding, italics, borders, shading, and superscripted and subscripted text, will not be used in the TLFs, unless otherwise specified. On some occasions, superscripts 1, 2, or 3 may be used (see below).
- Only standard keyboard characters will be used in the TLFs. Special characters, such as non-printable control characters, printer-specific, or font-specific characters, will not be used.
 Hexadecimal-derived characters will be used, where possible, if they are appropriate to help display math symbols (e.g., μ). Certain subscripts and superscripts (e.g., cm², C_{max}) will be employed on a case-by-case basis.
- Mixed case will be used for all titles, footnotes, column headers, and programmer-supplied formats, as appropriate.

16.2.2. Headers

- All output should have the following header at the top left of each page:
- Galderma Protocol RD.06.SPR.116912
- CC

Sponsor: Galderma Research & Development, LLC; Protocol No.: RD.06.SPR.116912, Version 6.0

- Draft/Final Run <date>
- All output should have Page n of N at the top or bottom right corner of each page. TFLs are
 internally paginated in relation to the total length (i.e., the page number should appear
 sequentially as page n of N, where N is the total number of pages in the table).
- The date output was generated should appear along with the program name as a footer on each page.

16.2.3. Display Titles

• Each TFL are identified by the designation and a numeral. (i.e., Table 14.1.1). ICH E3 numbering is strongly recommended, but sponsor preferences are obtained before final determination. A decimal system (x.y and x.y.z) are used to identify TFLs with related contents. The title is centered. The analysis populations are identified on the line immediately following the title. The title and table designation are single spaced. A solid line spanning the margins will separate the display titles from the column headers. There will be 1 blank line between the last title and the solid line.

Table x.y.z

First Line of Title

Second Line of Title if Needed

ITT Population

16.2.4. Column Headers

- Column headings are displayed immediately below the solid line described above in initial uppercase characters.
- In the case of efficacy tables, the variable (or characteristic) column will be on the far left followed by the dose group column (Nemolizumab 30 mg).
- For numeric variables, include "unit" in column or row heading when appropriate.
- Analysis population sizes will be presented for dose group in the column heading as (N=xx) (or in the row headings, if applicable). This is distinct from the 'n' used for the descriptive statistics representing the number of subjects in the analysis population.

16.2.5. Body of the Data Display

16.2.5.1. General Conventions

Data in columns of a table or listing are formatted as follows:

- Alphanumeric values are left-justified;
- Whole numbers (e.g., counts) are right-justified; and
- Numbers containing fractional portions are decimal aligned.

16.2.5.2. Table Conventions

- Units will be included where available
- If the categories of a parameter are ordered, then all categories between the maximum and
 minimum category are presented in the table, even if n=0 for dose group in a given category that is
 between the minimum and maximum level for that parameter. For example, the frequency
 distribution for symptom severity would appear as:

Severity	N
Rating	
severe	0
moderate	8
mild	3

Where percentages are presented in these tables, zero percentages will not be presented and so counts of 0 will be presented as 0 and not as 0 (0.0).

- If the categories are not ordered (e.g., Medical History, Reasons for Discontinuation from the Study, etc.), then only those categories for which there is at least 1 subject represented are included.
- An Unknown or Missing category are added to each parameter for which information is not available for 1 or more subjects.
- Unless otherwise specified, the estimated mean and median for a set of values are printed out to 1 more significant digit than the original values, and standard deviations are printed out to 2 more significant digits than the original values. The minimum and maximum should report the same significant digits as the original values. For example, for systolic blood pressure:

n	XX
Mean	XXX.X
SD	X.XX
Median	XXX.X
Min	XXX
Max	XXX

- Percentage values are printed to one decimal place, in parentheses with no spaces, one space after the count (e.g., 7 (12.8), 13 (5.4)). Pre-determine how to display values that round down to 0.0. A common convention is to display as '<0.1', or as appropriate with additional decimal places. Unless otherwise noted, for all percentages, the number of subjects in the analysis population for the treatment group who have an observation will be the denominator. Percentages after zero counts should not be displayed and percentages equating to 100% are presented as 100.0.

- Tabular display of data for medical history, prior/concomitant medications, and all tabular displays
 of adverse event data are presented by the body system, treatment class, or SOC. Within the

body system, drug class and SOC, medical history (by preferred term), drugs (by ATC code), and adverse events (by preferred term) are displayed in alphabetically order. If incidence for more than 1 term is identical, they should then be sorted alphabetically. Missing or not calculated descriptive statistics or p-values which cannot be estimated are reported as "-".

- The percentage of subjects is normally calculated as a proportion of the number of subjects
 assessed in the relevant treatment group (or overall) for the analysis population presented.
 However, careful consideration is required in many instances due to the complicated nature of
 selecting the denominator, usually the appropriate number of subjects exposed. Describe details
 of this in footnotes or programming notes.
- For categorical summaries (number and percentage of subjects) where a subject can be included
 in more than one category, describe in a footnote or programming note if the subject are included
 in the summary statistics for all relevant categories or just 1 category and the criteria for selecting
 the criteria.
- Where a category with a subheading (such as system organ class) has to be split over more than
 one page, output the subheading followed by "(cont)" at the top of each subsequent page. The
 overall summary statistics for the subheading should only be output on the first relevant page.

